5. STUDY POPULATION

5.1. Number of Subjects and Centers

A total of [REDACTED] are required to complete this study. To allow for discontinuations, up to a maximum [REDACTED] with PED resulting from a severe chemical and/or thermal injury will be randomized. The study will be conducted at [REDACTED]

5.2. Inclusion Criteria

A subject will be eligible for inclusion in this study only if ALL of the following criteria apply:

1. Male and female of any age.
2. Clinically non-infected, corneal persistent epithelial defect (PED) as a result of a severe chemical and/or thermal ocular injury in one or both eyes.
3. [REDACTED]
4. [REDACTED]
5. Providing written informed consent and ability to comply with the visit and dosing schedule.

NOTES:

- [REDACTED]
- [REDACTED]
- [REDACTED]
- [REDACTED]

5.3. Exclusion Criteria

A subject will not be eligible for inclusion in this study if ANY of the following exclusion criteria apply:

1. [REDACTED]
2. Have active clinically significant ocular infection.
3. Subjects with corneal perforation or impending corneal perforation.
4. Subjects with any other past or present ophthalmic disease or medical condition that, in the Investigator's opinion, may affect the safety of the subject or the outcome of the study.
5. Treatment with systemic corticosteroids

6. Subjects with severe lid abnormalities as a result of the injury contributory to the persistence of the epithelial defect such as inability to close the lids.
7. Subjects with a history of severe ocular conditions contributory to the persistence of an epithelial defect prior to the injury.
8. Female subjects of childbearing potential who are pregnant, nursing, planning a pregnancy or not using an adequate and medically acceptable form of birth control. An adult woman is considered to be of childbearing potential unless she is a) post-menopausal (defined as at least 12 months of amenorrhea), b) surgically sterilized and at least 3 months post-surgical, or c) using a hormonal contraceptive, intra-uterine device, diaphragm with spermicide, or condom with spermicide for the duration of the study.
9. Subjects who have participated in an interventional clinical trial within 30 days prior to Day 1.

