Inclusion/Exclusion Criteria	
INCLUSION CRITERIA
 
A subject will be eligible for inclusion in this study only if ALL of the following criteria apply:
 
1. Male and female of any age.2. Clinically non-infected, corneal persistent epithelial defect (PED) as a result of a severe chemical and/or thermal ocular injury in one or both eyes.3. [REDACTED]4. [REDACTED]5. Providing written informed consent and ability to comply with the visit and dosing schedule.

	
NOTES:
 
■ [REDACTED]■ [REDACTED]■ [REDACTED]■ [REDACTED]

EXCLUSION CRITERIA
 
A subject will not be eligible for inclusion in this study if ANY of the following exclusion criteria apply:
 
1. [REDACTED]2. Have active clinically significant ocular infection.3. Subjects with corneal perforation or impending corneal perforation.4. Subjects with any other past or present ophthalmic disease or medical condition that, in the Investigator's opinion, may affect the safety of the subject or the outcome of the study.5. Treatment with systemic corticosteroids [REDACTED] [REDACTED] [REDACTED]6. Subjects with severe lid abnormalities as a result of the injury contributory to the persistence of the epithelial defect such as inability to close the lids.7. Subjects with a history of severe ocular conditions contributory to the persistence of an epithelial defect prior to the injury.8. Female subjects of childbearing potential who are pregnant, nursing, planning a pregnancy or not using an adequate and medically acceptable form of birth control. An adult woman is considered to be of childbearing potential unless she is a) post-menopausal (defined as at least 12 months of amenorrhea), b) surgically sterilized and at least 3 months post-surgical, or c) using a hormonal contraceptive, intra-	

	
uterine device, diaphragm with spermicide, or condom with spermicide for the duration of the study.
 
9. Subjects who have participated in an interventional clinical trial within 30 days prior to Day 1.

--	--

Figure 1: 

[figure not shown]

TABLE 1: [REDACTED]

[figure not shown]
[figure not shown]

Figure 2: [REDACTED]

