5.4. Other Eligibility Criteria Considerations

To assess any potential impact on subject eligibility with regards to safety, the Investigator must refer to the latest edition of the Investigator's Brochure for NEXAGON – Ocular Administration, for detailed information regarding warnings, precautions, contraindications, adverse events and other significant data pertaining to the investigational product being used in this study.

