6.3. Urine Pregnancy Test

Urine pregnancy tests will be performed on all female subjects of childbearing potential immediately PRIOR to randomization on Day 1 BEFORE application of investigational product. **The test must be confirmed as negative before randomization.** Another final pregnancy test will be performed when the subject re-epithelizes or when the subject exits the study due to non-healing of the PED or another reason.

In the event of pregnancy, the subject will be withdrawn from the study and the pregnancy will be followed up to term for safety evaluation.

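### Exclusion 8 defines adult women on four reversible contraceptives as not of childbearing potential, so on the visible text no Day 1 pregnancy test is required for them and exclusion 8's nursing bar does not reach them

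*Protocol*

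**What the plan says.** Exclusion 8 in protocol Section 5.3 opens with the group it covers: "Female subjects of childbearing potential who are pregnant, nursing, planning a pregnancy or not using an adequate and medically acceptable form of birth control". The definition of that group follows: "An adult woman is considered to be of childbearing potential unless she is a) post-menopausal", with menopause taken as a year or more without periods. The second way out of the group is "b) surgically sterilized and at least 3 months post-surgical". The third way out, limb c), reads: "or c) using a hormonal contraceptive, intra-uterine device, diaphragm with spermicide, or condom with spermicide for the duration of the study". The synopsis repeats the criterion with the same three limbs.

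Section 6.3 uses the same term to say who is tested: "Urine pregnancy tests will be performed on all female subjects of childbearing potential immediately PRIOR to randomization on Day 1". The result must be negative before randomization. Section 6.3 also calls for a final test at re-epithelialization or at exit, in a sentence that names no class.

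Other provisions touch pregnancy. Section 6.3 withdraws a pregnant subject and follows the pregnancy to term, and Section 8.1.1 lists pregnancy as a mandatory withdrawal. Section 6.4 makes a positive pregnancy test the one laboratory result that excludes by rule, with no limit to any class. Exclusion 4 gives the Investigator discretion: "Subjects with any other past or present ophthalmic disease or medical condition that" might affect safety or outcome can bar entry. Section 5.4 adds a pointer to the Investigator's Brochure: "To assess any potential impact on subject eligibility with regards to safety, the Investigator must refer to the latest edition". Inclusion 1 admits both sexes at any age.

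**The concern.** Using a reversible contraceptive does not make a woman unable to conceive, and starting one does not show that she is not already pregnant. Limb c) looks like a list of acceptable birth control that has ended up in the definition of who cannot become pregnant. Because the eligibility criterion and the test both depend on that definition, the slip removes safeguards from the fertile women most likely to enrol.

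Two safeguards are at stake. One is the baseline test that would detect an unrecognized pregnancy before the first application. An unhealed subject can go on to another masked application and then open-label salvage at the highest concentration (Section 1.4.2), and the only later test that Section 6.3 describes is at re-epithelialization or exit. The other is the exclusion of nursing women, which has no fallback that names nursing in the visible text.

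**Working it through.** No arithmetic applies; the check is to follow the definition through the text.

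1. *Scope of exclusion 8.* The words about childbearing potential come first and govern all four conditions: pregnant, nursing, planning a pregnancy, and no adequate contraception.
2. *Effect of limb c).* The definition says every adult woman is in the class unless a), b) or c) holds. A user of hormonal contraception, an intra-uterine device, or a diaphragm or condom with spermicide meets c) and leaves the class.
3. *Day 1 test.* Section 6.3 requires it for the class. She is outside the class, so neither the test nor the negative result is required of her.
4. *Nursing.* Exclusion 8 is the only visible text that bars nursing, and it does not reach her. Nor does it reach a nursing woman sterilized at least 3 months ago, who leaves through limb b).
5. *The other two conditions.* Little is lost on planning a pregnancy or lacking contraception, since limb c) itself requires use throughout the study.
6. *Waiting time.* Limb b) asks for 3 months since surgery; limb c) asks for none. A woman sterilized less than 3 months ago stays in the class, while one who began a listed method on the day of entry leaves it at once.

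The result for the adult women who matter here, on the visible text:

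| Status | Day 1 test required now | Nursing barred by exclusion 8 now | After the fix |
|---|---|---|---|
| One of the four listed methods | No | No | Test required; nursing barred |
| Another adequate method | Yes | Yes | Unchanged |
| Sterilized at least 3 months | No (not needed) | No | No test; nursing barred |

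Women with no adequate method are excluded outright. Among fertile adult women who can enter, the required test therefore reaches only those whose method is not on the list, which is hard to see as intended.

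*Do other provisions close the gap?* The withdrawal rules in Sections 6.3 and 8.1.1 start once a pregnancy is known. Section 6.4 acts on a positive result but orders no test for her. Exclusion 4 and Section 5.4 rest on the Investigator's judgement, and neither orders a test or mentions nursing.

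**The case against.** The strongest reply is that much of the relevant text is hidden. Table 1, inclusion criteria 3 and 4, the inclusion notes, exclusion 1 and the list of tests in Section 6.4 are redacted, and any of them could hold a pregnancy or nursing rule. Section 4.1 sends sites to Table 1 as well as Section 6. This stands. Section 6.3 says who must be tested but does not say that nobody else may be, so a Table 1 entry testing all females would add to it without contradicting it. That is why confidence is medium.

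A second reply is that pregnancy is handled elsewhere. This stands in part. A reader might infer that the plan lets known pregnant women enter. The documents do not support that: a positive test excludes any subject, a pregnant subject is withdrawn, and a woman known to be pregnant would hardly be recorded as a contraceptive user. The gap on pregnancy is the unrecognized one, and it is the same gap as the missing Day 1 test, so it should be counted once.

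A reader might also infer that the final test is lost. That sentence refers simply to the subject. Reading it with the same class is natural, but it is inference and is not counted as a loss here.

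Third, sites may see limb c) for what it probably is and test these women anyway. Some may, but then practice depends on which sites correct the definition for themselves.

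Finally, no fetal or nursing harm is shown. Section 1.2.1 reports no toxicity on local and systemic evaluation, and whether reproductive studies were done cannot be seen. The point does not need such evidence: the plan has already decided that pregnant and nursing women should not be treated, and its wording does not carry that out.

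**Conclusion.** The point holds on the visible text, with medium confidence. For an adult woman on any of the four listed methods, the Day 1 test is not required and exclusion 8's nursing bar does not apply; a nursing woman sterilized at least 3 months ago also escapes that bar. Known pregnancies and positive tests are still acted on.

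The size cannot be given as a head count or percentage, because the documents do not state contraceptive use and the sample size is redacted. The affected women are by definition using contraception, which limits the pregnancy risk but does nothing for nursing. The primary analysis is unaffected. This is a moderate patient-safety correction to eligibility wording that should be made.

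The conclusion assumes that limb c) is applied as written and that no redacted table or criterion supplies the missing test or a separate nursing rule.

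**What to change.** Reword exclusion 8 in three parts:

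1. Exclude every female subject who is pregnant or nursing, whatever her childbearing status.
2. Exclude females of childbearing potential who plan a pregnancy or do not use adequate birth control throughout the study. Move the four methods here as examples.
3. Define childbearing potential by limbs a) and b) only, and delete limb c).

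State in Section 6.3 that both the Day 1 and the final test apply to this class, and align the synopsis and Table 1. As an optional clarification, since inclusion 1 admits any age and the definition speaks only of adult women, extend it to post-menarchal minors.

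Deleting limb c) alone would restore the Day 1 test but would still let a nursing woman sterilized at least 3 months ago through, so part 1 is needed as well.

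The cost is up to two urine tests per affected woman (Day 1 and final), using a test already in the protocol, and an amendment with the national and local approvals that Section 11.13 requires. Women on a listed method stay eligible unless they are pregnant, nursing or planning a pregnancy. If Table 1 already tests all females, the amendment only brings the wording into line.

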5.4. Other Eligibility Criteria Considerations

To assess any potential impact on subject eligibility with regards to safety, the Investigator must refer to the latest edition of the Investigator's Brochure for NEXAGON – Ocular Administration, for detailed information regarding warnings, precautions, contraindications, adverse events and other significant data pertaining to the investigational product being used in this study.

5.5. Prior and Concomitant Medications

All medical and surgical treatments/procedures for the PED since the original chemical and/or thermal injury should be recorded and transcribed into the CRF.

A record will be kept of all medication administered, surgical procedures undertaken and supplements used by subjects since the time of injury and PRIOR to study enrollment.

Similarly, over the course of the study FOLLOWING enrollment, a record will be kept of all concomitant medication administered, procedures undertaken and supplements used by subject until study exit will also be recorded. Subjects must be questioned at each study visit concerning any new medications or changes in current medications including over-the-counter medication.

For each medication taken or procedure performed, the following information will be collected:

- Medications generic name/procedure name
- Eye that was treated, if applicable
- Indication for the medication/procedure
- Dose, route and frequency of administration of medication
- Date started medication/date of procedure
- Date stopped medication

5.5.1. Standard of Care - Topical Ocular Concomitant Medications

Over the course of the study, from baseline assessments through to study completion, subjects will continue to receive the standard of care regimen prescribed to them by their Investigator. The standard of care should remain unchanged until re-epithelialization or study exit if re-epithelialization is not achieved. Details will be recorded on the prior and concomitant medication case report form.

The only exception will be on study days where IP is to be administered. On these days, it is important for the Investigator or delegate to advise the subject [REDACTED]

[REDACTED]

[REDACTED]

[REDACTED]

[REDACTED]

[REDACTED]

[REDACTED]

[REDACTED]

Patching: Is only required as indicated post application of the investigational product.

[REDACTED]

[REDACTED]

[REDACTED]

Therapy considered necessary to a subject's welfare may be given at the discretion of the Investigator but prior to application this should first be discussed with the Medical Monitor or Sponsor representative.

Systemic standard of care will not be defined by the protocol but by the Investigator's or study site routine practice. However, systemic medications and regimen for the treatment of the PED should remain unchanged for the duration of the study, until re-epithelialization or study exit. Details must be recorded in the source documents and the CRF.

5.5.2. Prohibited Medications

Medications to be avoided over the course of the study are:

• [REDACTED]

[REDACTED]

- [REDACTED]
- [REDACTED]

6. STUDY ASSESSMENTS AND PROCEDURES

6.1. Informed Consent

Written informed consent will be obtained for this study by the Principal Investigator or suitably qualified designee from all subjects before any protocol-specific procedure can be performed.

This study will be conducted in accordance with the provisions of the Declaration of Helsinki.

In obtaining and documenting informed consent, the Investigator must comply with applicable regulatory requirements and must adhere to Good Clinical Practice (GCP). The Investigator must fully inform subjects of all pertinent aspects of the study. Before informed consent may be obtained, the Investigator, or a person designated by the Investigator, must provide the subject ample time and opportunity to inquire about details of the study and to decide whether or not to participate in the trial. All questions about the trial must be answered to the satisfaction of the subject. Prior to the subject's participation in the trial, the written informed consent must be signed and personally dated by the subject and by the person who conducted the informed consent discussion. For additional information, please refer to [Section 11.3](#).

6.2. Demography

PRIOR to Day 1 when eligibility is being assessed, the following will be collected on the CRF:

- Gender
- Ethnicity
- Race, and
- Date of birth

6.3. Urine Pregnancy Test

Urine pregnancy tests will be performed on all female subjects of childbearing potential immediately PRIOR to randomization on Day 1 BEFORE application of investigational product. **The test must be confirmed as negative before randomization.** Another final pregnancy test will be performed when the subject re-epithelizes or when the subject exits the study due to non-healing of the PED or another reason.

In the event of pregnancy, the subject will be withdrawn from the study and the pregnancy will be followed up to term for safety evaluation.

6.4. Clinical Laboratory Tests

Routine blood laboratory tests will be performed BEFORE application of investigational product. Baseline blood samples may be done during the Eligibility Assessments OR prior to randomization on Day 1.

These baseline laboratory results will serve as a record for subjects on study entry, enable comparison with results on study exit post treatment (whether healing occurred or not) and enable Investigators to

make an informed assessment of any adverse events or serious adverse events, that may occur during the study.

NO specific laboratory results (other than a positive pregnancy test) will be used to exclude a subject from entry or continued participation in the study, unless in the Investigator's opinion the results indicate the subject has a concurrent condition that may affect the safety of the subject or potentially the outcome of the study ([Exclusion Criteria 5](#)).

The same blood tests will be repeated when the subject completes the Treatment Period of the study. Refer to [Table 1](#) - Schedule of Assessments. A sample of up to [REDACTED] will be collected at each timepoint and the sample prepared as detailed in the Laboratory Manual.

The tests to be performed are as follows:

- [REDACTED]
- [REDACTED]

6.5. Medical History and Concomitant Medication

A medical history, including details of any ongoing medical conditions, will be recorded PRIOR to Day 1 and before eligibility is confirmed. Aside from being used to determine subject eligibility, this information will permit the Investigator to record the nature, duration and severity of any ongoing baseline medical conditions prior to randomization and receiving investigational product treatment. **All medications that are used during a subject's participation in the study must be recorded in the source documents and transcribed onto the CRF.**

6.6. Ocular History and Eligibility Assessments Prior to Day 1 and Prior to Randomization Day 1

A detailed ocular examination and history will be conducted **PRIOR to the Day 1 visit** and assessed against the inclusion and exclusion criteria of this protocol. For subjects with a bilateral ocular injury, both eyes should be assessed.

Specific information regarding the etiology and prior history of the PED must be recorded as follows:

- Cause of the defect;
- Date when the defect first appeared (regarded as the first day of injury);
- Medications and/or surgical procedures that have been used to treat the PED, including non-prescription therapies, since injury;
- Measurements of the defect to enable assessment of epithelial defect responsiveness to standard of care;
- Classification of the lesion using the Dua grading scale as detailed in [Appendix 1](#).

Other assessments will include:

[figure not shown]
- Ocular symptoms questionnaire – to record severity of symptoms
- Ocular Injury - Physician Assessment
- Visual acuity
- Biomicroscopy

- PED assessment including digital photography
- Ophthalmoscopy

On Day 1, prior to randomization, the following assessments will include:

- Ocular symptoms questionnaire
- Ocular Injury - Physician Assessment
- Visual acuity
- [REDACTED]
- PED assessment including digital photography

Refer to [Table 1](#) - Schedule of Assessments for assessments prior to and on Day 1.

6.7. Ocular Assessments following Randomization

Once eligibility is confirmed the following assessments will be conducted at all further study visits, unless otherwise specified. If investigational product is to be administered at a study visit, the ocular assessments MUST be conducted PRIOR to investigational product application. In addition, the Ocular Symptoms Questionnaire and Ocular Pain Measurement Rating Scale which both involve subject responses should be conducted before other ocular assessment are conducted by the Investigator or delegate.

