1.2.2. Effects in Humans – Clinical Summary

The safety, tolerability and clinical effects of topical administration of NEXAGON have been investigated in four Phase 1 studies (one ocular and three dermal) and three dermal Phase 2 studies in venous leg ulcer and diabetic foot ulcer patients.

Human clinical experience with NEXAGON to date has indicated that NEXAGON has an excellent safety profile and is well tolerated. The only adverse events reported as being possibly related to NEXAGON were transient sensations of stinging/tingling/burning when administered to chronic venous ulcers (3 patients in total). No other possibly related or related adverse events or serious adverse events have been reported to date in any of the clinical studies and the 12 compassionate use patients.

Details of the ocular clinical studies and the isolated compassionate use for ocular applications are described in more detail in the latest edition of the Investigator's Brochure for NEXAGON® – Ocular Administration.

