1.4. Dose Concentration, Administration and Regimen Rationale

NEXAGON is formulated with two components, namely the active pharmaceutical ingredient (API), called CODA001 which is an unmodified [REDACTED] oligonucleotide [REDACTED]
[REDACTED]

NEXAGON [REDACTED] have been selected as the two dose concentrations to be used in this study. The comparator will be the Vehicle [REDACTED]
[REDACTED].

The primary endpoint will be corneal epithelial recovery, [REDACTED]
[REDACTED]

Previous dosing experiences of NEXAGON in ocular indications are as follows:

- **Study NEX-OCU-001:** A Phase 1, dose-rising safety study in 26 participants which assessed the safety of [REDACTED] of [REDACTED] of NEXAGON applied to the de-epithelialized eye following photo-refractive keratectomy. There were no side effects or dose-limiting toxicities attributable to any dose of NEXAGON in any of these subjects in this study. Therefore, all four dose concentrations were safe and tolerated when applied to a wounded human eye.
- **Study NTX-OCI-001:** A Phase 2 randomized, prospective, double-masked, vehicle-controlled study to evaluate the safety and efficacy of topical NEXAGON in subjects with ocular surface chemical burns. Subjects were randomized to either NEXAGON ([REDACTED]

[REDACTED] the equivalent volume of NEXAGON Vehicle. Investigational product was given on [REDACTED] in addition to the subjects receiving standard of care. Clinical doses of [REDACTED] was chosen largely based on the previous Phase 1 study and the anticipated effect of standard of care on NEXAGON application. No overt toxicity was seen in NEX-OCU-001 [REDACTED] or in the animal toxicology studies up to 32 mg/mL (3.2%) per eye. The study was closed due to slow enrollment after a total of 34 of 66 subjects were recruited, analysis of the data indicated that further investigation of the effects of NEXAGON in patients with severe ocular burns that are more difficult to heal was warranted in a subsequent trial.

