APPENDIX 2:

Determine the severity and frequency of each symptom in the study eye (if bilateral injury, also the fellow eye) by questioning the subject with regard to the following:

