APPENDIX 3: [REDACTED]

At each scheduled visit, the Visual Analogue Scale, below, will be completed by the subject to rate the intensity of the pain being experienced by the subject in the study eye (if bilateral injury, also the fellow eye) at that moment in time.

[REDACTED]

[REDACTED]

[REDACTED]

[figure not shown]
[REDACTED]

[REDACTED]

[REDACTED]

[figure not shown]

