Separate summaries of TEAEs will be provided showing the number and percentage of subjects who experienced at least one TEAE by treatment group and over all subjects. Non-ocular TEAEs will be summarized using discrete summary statistics and presented by treatment group at the subject and event level by SOC and PT. Ocular TEAEs will be similarly summarized at the subject level for study and fellow eyes separately. If a subject reports the same PT multiple times within the same SOC, that PT will only be reported once within that SOC. As with the PT, if a subject reports multiple conditions within the same SOC, that SOC will only be reported once. In the summary, SOCs will be listed in ascending alphabetical order; PTs will be listed in order of descending frequency for all subjects within each SOC.

The number of subjects with any TEAEs (along with percentages) will be tabulated by SOC and PT within each SOC by treatment group. Summaries of TEAEs by maximal severity, strongest relationship to study drug, and strongest relationship to study drug and maximal severity will be presented for ocular AEs and non-ocular AEs separately. To count the number of subjects with any TEAEs, if a subject has multiple TEAEs coded to the same PT within the same SOC, the subject will be counted once under the maximum severity. TEAEs that led to test article discontinuation, defied as drug interruption or drug withdrawal as response to the AE, treatment related TEAEs, and TE-SAEs will also be summarized by SOC and PT.

15.2

[REDACTED]

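### The pain scale is rated before each application and for the current moment only, so it cannot show application reactions, and the study-eye TEAE table by preferred term has no event counts (minor)

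*Protocol*

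**What the plan says.** Protocol 6.7 fixes the order of work on a dosing day: "If investigational product is to be administered at a study visit, the ocular assessments MUST be conducted PRIOR to investigational product application". It adds that "the Ocular Symptoms Questionnaire and Ocular Pain Measurement Rating Scale which both involve subject responses should be conducted before other ocular assessment", so the two subject-reported measures come first of all. Appendix 3 has the subject rate pain in "the study eye (if bilateral injury, also the fellow eye) at that moment in time". Appendix 2, the symptom questionnaire, is worded differently: "Determine the severity and frequency of each symptom in the study eye". Its items and recall period are not shown.

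AEs are collected separately. Protocol 9.1 records them from the first application to the final visit, and Protocol 4.1 has TEAEs assessed at each study visit. The Synopsis (Study Description) sets visits twice weekly until healing and has the eye padded and taped shut after the first application.

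In SAP 15.1, non-ocular TEAEs are summarized by system organ class (SOC) and preferred term (PT) at both subject and event level. For the eye the text is "Ocular TEAEs will be similarly summarized at the subject level for study and fellow eyes separately", and a repeated PT is reported once per subject. The overall TEAE summary in the same section does include the number of events, with a study-eye breakdown.

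On prior experience, Protocol 1.2.2 says the only events reported as possibly related to NEXAGON were "transient sensations of stinging/tingling/burning when administered to chronic venous ulcers (3 patients in total"). For the ocular Phase 1 study of 26 participants, Protocol 1.4 says: "There were no side effects or dose-limiting toxicities attributable to any dose of NEXAGON in any of these subjects in this study".

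**The concern.** Safety of two concentrations is part of the study objective, and the product is applied repeatedly to severely injured eyes. The events that earlier use did turn up were brief and arose on administration. A tolerability signal of that kind would appear shortly after application, and the pain scale is never rated then. If pain scores show no difference between arms, a reader of the results could take that as evidence of comfort on application, when the scores mainly follow the course of the injury.

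The tabulation adds to this. For a product applied to the eye, the treated eye gets less detail by preferred term than the rest of the body. A subject whose eye burns at every application and one whose eye burned once appear identically in the study-eye SOC/PT table, and no readable table ties onset to an application.

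**Working it through.** The plan states no figure that bears on this point, so the check is mainly a comparison of the texts.

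**1. Pain scale.** Protocol 6.7 places it before application. Appendix 3 limits it to the present moment. Together these mean that no dosing-day pain rating reflects that day's application. The next rating is at the next visit. With two visits a week the mean gap is 7/2 = 3.5 days, that is 3 to 4 days, unless the missing schedule (Protocol Table 1) holds another visit. A transient reaction would be over by then.

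**2. Symptom questionnaire.** It has the same pre-application timing, but it asks about frequency as well as severity, which may imply a look-back. With no recall period shown, the conclusion in step 1 cannot be extended to it.

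**3. AE enquiry.** The order rule in 6.7 governs the ocular assessments in 6.7.1 to 6.7.8, and AE enquiry is not among them. Nothing readable places it before application, and nothing readable places it after.

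**4. Tabulation (SAP 15.1).**

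| Output | Subjects | Events | By PT | Linked to application |
|---|---|---|---|---|
| Overall summary, study eye | yes | yes | no | no |
| Non-ocular SOC/PT | yes | yes | yes | no |
| Study-eye SOC/PT | yes | no | yes | no |

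The gap is the study-eye event count by preferred term, together with the link to application.

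**5. Size of what the table drops (illustration).** Assume k applications per subject (k = 2 to 4, because the number is redacted) and an independent reaction probability p at each. Events per subject are k × p. Subject incidence is 1 − (1 − p)^k. The ratio of events to affected subjects is kp / [1 − (1 − p)^k]. For k = 4 and p = 0.10 this is 0.40 / 0.344 = 1.16.

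| k | p = 0.05 | p = 0.10 | p = 0.30 | p = 1 |
|---|---|---|---|---|
| 2 | 1.03 | 1.05 | 1.18 | 2.0 |
| 3 | 1.05 | 1.11 | 1.37 | 3.0 |
| 4 | 1.08 | 1.16 | 1.58 | 4.0 |

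The number of affected subjects is the same whether or not events are counted; only repeat episodes disappear. Where reactions are uncommon (p up to 0.10), event counts add 3% to 16%. At p = 0.30 they add 18% to 58%. If every application causes a reaction, the event count is k times the subject count.

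**The case against.** The case on the other side is strong, and most of it stands.

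- Pre-application rating is sensible for a measure that follows healing, and SAP 14.3 places change in ocular symptoms among the exploratory analyses. A healing measure is not defective because it does not detect application discomfort.
- Application takes place at study visits. A subject whose eye burns at that moment can be recorded as having an AE there and then. A reader might infer that AE capture depends on recall several days later. The documents do not say so; the 3 to 4 day gap belongs to the pain scale.
- A reader might infer that the questionnaire is equally blind to application reactions. Its frequency wording and unseen recall period do not support that.
- A reader might infer that study-eye events are counted nowhere, or that TEAE incidence will come out too low. The overall summary counts events for the study eye, all TEAEs are listed, and counting a subject once per PT leaves incidence unchanged.
- A reader might infer that NEXAGON has an established reaction in the eye. The reported events were in three patients with venous leg ulcers and were rated only possibly related, and the ocular Phase 1 study attributed none. The rate in severely injured eyes is unknown, which is not the same as shown to be nil.
- Protocol Table 1, much of Protocol 7.4.4 and SAP 15.2 are not visible, and the SAP table list has gaps. A post-application check or a further table may already be planned.

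What remains is the pre-dose pain scale without recall, the absence of any readable post-application AE enquiry, and the missing event column for the study eye.

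**Conclusion.** The point holds in a limited form and is minor. On the legible text, the pain results cannot register a transient reaction to the day's application and should not be cited as evidence of application tolerability. The study-eye SOC/PT table loses repeat episodes, and no readable output shows application-day reactions by arm. The stated safety endpoint, incidence of TEAEs, is not biased by this.

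The size of the loss cannot be taken from the documents, because the number of applications is redacted and no ocular reaction rate is given. The ratios above rest on assumed k and p and on independence between applications. The conclusion on AE enquiry also assumes that the redacted text adds no post-application check. If it does, only the tabulation point and the caution on interpreting the pain scores remain.

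**What to change.** **SAP 15.1.** Add event counts to the study-eye SOC/PT table, matching the non-ocular one. Add one table by arm of study-eye TEAEs whose onset date equals an application date, giving subjects with at least one such event and events per application. The per-application rate is useful because subjects who heal early receive fewer applications, so the arms may differ in exposure. The inputs are AE onset dates and Listing 16.2.5 (Investigational Product Administration). The match is by date, so it may include an event that began earlier the same day; a footnote should say so.

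**Protocol 6.7.** Keep the pre-application ratings. State that the existing AE question is asked again after each application, before the subject leaves, and that any reaction is recorded with that day's onset date. If a redacted section already provides this, a cross-reference is enough. The question is verbal and does not require the eye to be uncovered.

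**Cost.** One column, one table and one protocol sentence, plus about a minute of site time per application. No dose, schedule or efficacy rating changes. The downside is that more mild, transient ocular TEAEs will be recorded in all arms, including Vehicle.
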